# PROTOCOL SYNOPSIS

**TITLE:** A PHASE II STUDY OF R-CHOP WITH INTENSIVE CNS PROPHYLAXIS AND SCROTAL IRRADIATION IN PATIENTS WITH PRIMARY TESTICULAR DIFFUSE LARGE B-CELL LYMPHOMA (DLBCL)

## AIM

To assess the feasibility, activity and safety of a therapeutic program in which patients with testicular large cell lymphoma receive state-of-the-art chemo-immunotherapy plus both intrathecal (with liposomal cytarabine) and systemic CNS prophylaxis (with intermediate-dose methotrexate), followed by locoregional radiotherapy.

## PATIENT POPULATION

- Primary testicular DLBCL
- Ann Arbor stage I-II at presentation (including bilateral testis involvement)
- untreated disease
- bidimensionally measurable, evaluable or no evidence of disease
- age 18-80 years
- ECOG performance status  $\leq 2$

## STUDY DESIGN AND STATISTICAL RATIONALE

Phase II non comparative study aimed to determine the feasibility and toxicity of the R-CHOP regimen in combination with intrathecal liposomal cytarabine and systemic intermediate-dose methotrexate followed by loco-regional radiotherapy. The previous IELSG 5 retrospective analysis on 373 patients with testis lymphoma, showed a PFS of 48% at 5 years in the entire population, regardless of the type of treatment. The IELSG 10 prospective clinical study was designed with a sample size of 50 patients defined to reject the null hypothesis of a PFS of 50% under the alternative hypothesis that the true PFS is 70% with a 5% significance level (two-sided) and 80% power.

The early results of IELSG 10 study seem to suggest that Rituximab-CHOP regimen plus intrathecal prophylaxis with methotrexate may reduce the incidence of CNS relapses and, therefore, improve the outcome. However, the follow up is not yet adequate to allow any sound conclusion and, at present, it is unclear on which estimation of PFS should a sample size be calculated. According to the recruitment rate of the previous IELSG 10, assuming a similar number of participating centers, we may expect to enroll approximately 35 cases in 4 years. At that point, the feasibility of the design should be adequately evaluated and the follow up data from the previous IELSG 10 study should be mature enough for a careful calculation of the sample size in order to transform this pilot study in a formal phase II trial.

## TREATMENT PROGRAM

WEEKS 1-15	- 6 cycles of CHOP on days 1 to 5, to be repeated q 21 days - Rituximab on day 0 or day 1 - IT chemotherapy: Depocyte®, 50 mg on day 0 of cycles 2, 3, 4, 5 of CHOP
WEEKS 18-22	- Methotrexate 1.5 g/m  q 14 days x 2
FROM WEEKS 24	- Scrotal prophylactic radiotherapy or involved field radiotherapy (but can be planned concomitantly to R-CHOP in patients with bilateral disease)

## SAFETY PARAMETERS

Clinical laboratory data, physical exams, observations for adverse events

## TIME PERIOD AND NUMBER OF PATIENTS

Starting Date of Study	March 2009
Completion Date	March 2013
Trial sample	35 patients will be enrolled over 36 months

# 1. INTRODUCTION

## 1.1. Background

### 1.1.1. Primary testicular lymphoma background

PTL is a rare disease that represents 1% to 2% of all non-Hodgkin's lymphomas, with an estimated incidence of 0.26/100,000 per year. 1 PTLs account for no more than 5% of all testicular malignancies, however they represent the most frequent testicular cancer in men older than 50 years of age. 2 PTL is a typically disease of elderly, 85% of PTLs are diagnosed in men over 60 years of age. 3 Histologically, 90% or more of PTLs are of diffuse large-cell type (DLBCL) with B cell phenotype.

PTL has a propensity to disseminate systematically to several extranodal sites including the contralateral testis, central nervous system (CNS 6% - 16%), skin (0% - 35%), Waldeyer's ring (5%), lung, pleura and soft tissue. Mainly, the portion of patients showing CNS involvement at diagnosis, 2% to 16%, is higher than in nodal lymphomas.3,6,7

Primary testicular lymphomas (PTL) are very aggressive malignancies with poor prognosis. Five year survival ranged from 16% to 50% and median survival has been reported of only 12-24 months according to the different series of patients.2,8,7 The use of anthracycline-based chemotherapy has been associated with a 5-yr survival of 30-60% in different series, nevertheless there is a continuous relapse pattern with no evidence of plateau in the survival curve.9,10,11,12,7 Doxorubicin-containing regimens has allowed an improvement in the relapse-free survival comparing orchietomy  $\pm$  radiotherapy, however the advantage on survival time varied a lot among the different series published so far.13,11,7 In the largest series of patients reported so far by the IELSG (373 patients), the outcome of patients was extremely poor with an actuarial 5- and 10-years OS of 48% and 27% and an actuarial 5- and 10-years progression free survival of 48% and 33% respectively. The survival and PFS curves showed no clear evidence of a plateau, suggesting no cure for patients affecting by primary testicular lymphoma, even for those presenting with stage I/II (5 and 10 yrs OS in stage I 58% and 29%, stage II 46% and 29%7, respectively). The majority of patients with PTL relapse despite complete response to initial treatment. When radiation is given to the retroperitoneal lymph nodes, failures are systemic. Very few cases of in-field relapses have been reported. After chemotherapy both systemic and regional relapses are seen. Most relapses occurred in the first two years, but late relapses have also been described.14,7 One of the peculiar feature of PTL is a contralateral testis relapse occurring in 5-35% of the patients.5 In the retrospective series of 373 patients reported by IELSG, the commonest sites of relapse were: CNS (5 and 10-years risk of CNS relapse 20% and 35%) and contralateral testis (15% at 3 years, 40% at 15 years) occurring in patients not receiving prophylactic scrotal radiotherapy.7 Prophylactic irradiation of the contralateral testis has been proved to successfully prevent testicular recurrences in some studies.13,7 In the IELSG study prophylactic radiotherapy to contralateral testis was also associated with better PFS (5-year PFS 36% vs 70%) and OS (5-year OS 38% vs 66%). Moreover, CNS relapses are definitely more common than in other aggressive lymphomas and they have been reported up to 30% of the patients within 1-2 years from diagnosis. However, late relapse have also been described, sometimes as CNS relapse alone.12,11 The high rate of CNS recurrence is troublesome and has led to a recommendation for routine CNS prophylaxis. Although the use of prophylactic intrathecal chemotherapy has been advocated, its value is controversial because CNS relapses occur more frequently in brain parenchyma than in meninges and also in patients who had received intrathecal chemotherapy.6,7 The best strategy to prevent CNS relapse is still a matter of debate.

As well demonstrated in nodal diffuse large B-cell lymphoma (DLBCL) , the addition of Rituximab to CHOP chemotherapy may be useful in PTL as suggested by preliminary data of IELSG10 study recently reported.16 In this study 45 patients with stage I-II PTL were treated with CHOP - Rituximab and CNS prophylaxis with 4 administrations of intrathecal methotrexate and scrotal radiotherapy  $\pm$  loco-regional radiotherapy for stage II. The preliminary results suggest an improvement in the outcome with a 3-year OS and EFS of 88% and 78%, no contralateral testis relapse and 2.5% actuarial risk of CNS relapse at three years. However the median follow-up is still short and systemic and CNS recurrence rate might increase with a longer follow-up. Perhaps the incorporation of chemotherapy agents that have a better penetration into the CNS, as intermediate/high-

dose methotrexate and/or intrathecal liposomal cytarabine, would allow a more effective control of the disease and may prevent CNS recurrence. A new prospective phase II study has been outlined aimed to further reduce systemic and CNS recurrence and, possibly, better define the standard treatment for PTL. Patients will receive state-of-the-art chemoimmunotherapy plus both intrathecal and systemic CNS prophylaxis.

### **1.1.2. Liposomal cytarabine (Depocyte) background**

Potential risks of depocyte.

The following adverse event occurring in two or more patients receiving DepoCyte in the phase III/IV clinical studies were associated with patient outcomes categorized as serious. The events are listed by descending order of frequency within body system.

Body as a Whole: headache, fever, asthenia, back pain, hydrocephalus, pain, sepsis, neoplasm, injection site reaction, infection, mucous membrane disorder, abdominal pain, chills, accidental injury

Nervous system: seizure, psychosis (hallucinations/delusions), confusion, arachnoiditis, intracranial hypertension, somnolence, meningitis, agitation, neuropathy, hypoesthesia, liquor alterations, dizziness, gait disorders, coma, subdural haematoma, meningism, facial paralysis.

Digestive system: nausea, vomiting, gastrointestinal haemorrhage, intestinal occlusion, diarrhoea, anorexia

Cardiovascular system: cardiac arrest, pulmonary embolus, hypotension, syncope, deep thrombophlebitis.

Hemic and Lymphatic system: neutropenia, thrombopenia, anaemia.

Metabolic and Nutritional Disorder: dehydration, hyperglycaemia, hyponatremia, alkalosis

Respiratory system: pneumonia, apnoea, dyspnoea, bronchitis

Special senses: deafness

Urogenital system: urinary tract infection

Skin and Appendages: sweating

### **1.1.3. Rituximab background**

Potential risks of rituximab.

The most serious adverse reactions with rituximab include: infusion reactions, tumor lysis syndrome, mucocutaneous reactions, hypersensitivity reactions, cardiac arrhythmias, angina, and renal failure. The incidence of clinically significant abdominal pain, anemia, dyspnea, hypotension and neutropenia was higher in subjects with bulky disease (lesions > 10 cm) vs subjects with lesions < 10 cm. During retreatment with rituximab the incidence of grade 3 and 4 adverse events was similar to the experience of patients receiving the first treatment (58% and 57% respectively).

Mild to moderate infusion reactions consisting of fever and chill/rigors occurred in the majority of patients during the first infusion. Other frequent infusion reaction symptoms included nausea, pruritus, angioedema, asthenia, hypotension, headache, bronchospasm, throat irritation, rhinitis, urticaria, rash, vomiting, myalgia, dizziness and hypertension. These reactions generally occurred within 30 to 120 minutes of beginning the first infusion and resolved with slowing or interruption of the rituximab infusion and with supportive care.

Rituximab induced B-cell depletion in 70-80% of patients and was associated with decrease serum immunoglobulins in a minority of subjects, infections events occurred in 31% of patients. Grade 3 and 4 infectious events including sepsis occurred in 25 of patients. Grade 3 and 4 cytopenia were reported in 485 of subjects, a single occurrence of transient aplastic anemia and 2 occurrence of hemolytic anemia were reported. In addition, there have been a limited number of postmarketing reports of pancytopenia, marrow hypoplasia and late onset neutropenia (defined as occurring 40 days after the last dose of rituximab) in patients with hematological malignancies. Grade 3 and 4 cardiac events including hypotension and rare fatal cardiac failure with symptomatic onset after rituximab administration have been reported. Pulmonary events were experienced by 38% of patients. The most common respiratory adverse events were increased cough, rhinitis, bronchospasm, dyspnea and sinusitis. In addition, immune/autoimmune events have been reported including uveitis, optic neuritis (in a subject with systemic vasculitis), pleuritis in a subject with lupus-like syndrome, serum sickness with polyarticular arthritis and vasculitis with rash.

Hepatitis B virus (HBV) reactivation with fulminant hepatitis, hepatic failure and death has been reported in some patients with hematological malignancies treated with rituximab. The majority of patients received rituximab in combination with chemotherapy. The median time to the diagnosis of hepatitis was

approximately 4 months after the beginning of rituximab and approximately 1 month after the last dose. Carriers of hepatitis B should be closely monitored for clinical and laboratory signs of active HBV infection and for signs of hepatitis during and for up to several months following rituximab therapy. In patients who develop viral hepatitis, rituximab and any concomitant chemotherapy should be discontinued and appropriate treatment including antiviral drugs should be initiated.

Two patients have died after being treated with rituxan for systemic lupus erythematosus (SLE). The cause of death was a viral infection of the brain called progressive multifocal leukoencephalopathy (PML) that is caused by reactivated JC virus. Latent JC virus is present in about 80 percent of adults. Rituxan is prescribed off-label for other serious disease and conditions such as SLE. The sponsor estimates that approximately 10,000 patients with SLE have been treated with Rituxan. Reactivation or exacerbation of viral infections including JC virus leading to PML may occur when patients receive Rituxan for any reason. Patients who have been treated with Rituxan and present or develop new neurological signs or symptoms should be evaluated for PML.

Less common adverse events (>1% and <5%) reported from clinical studies included agitation, anorexia, hypokinesia, hyperesthesia, hypoglycemia, injection site pain, insomnia, lacrimation disorder, malaise, nervousness, neuritis, neuropathy, paresthesia, somnolence, vertigo and weight decrease.

## **1.2. Overall rationale for the study**

A previous IELSG large retrospective analysis on 373 patients with testis lymphoma, showed a PFS of 48% at 5 years in the entire population, regardless of the type of treatment. A more recent IELSG prospective study has suggested that systemic doxorubicin regimens with rituximab and intrathecal prophylaxis with short acting methotrexate may improve the outcome but long term results are available only for a few patients and this approach reduces but does not eliminate CNS relapses. The incorporation of chemotherapy agents that have a better penetration into the CNS, as intermediate-dose methotrexate and intrathecal liposomal cytarabine which maintains cytotoxic concentrations of ara-C in the CSF for at least 14 days, would allow a more effective control of the disease and may prevent CNS recurrence.

## **2. OBJECTIVES**

### **2.1. Primary objective**

To demonstrate safety and feasibility of the R-CHOP regimen in combination with intrathecal liposomal cytarabine and systemic intermediate-dose methotrexate followed by loco-regional radiotherapy in untreated patient with stage I and II Primary Testicular Lymphoma

### **2.2. Secondary objectives**

To evaluate the efficacy of the R-CHOP regimen in combination with intrathecal liposomal cytarabine and systemic intermediate-dose methotrexate followed by loco-regional radiotherapy in prolonging 3-year Progression-Free Survival (PFS) and 3-year Event-Free-Survival (EFS) rate compared to historical standard treatment.

To evaluate 3-year overall survival of the patients treated with R-CHOP in combination with intrathecal liposomal cytarabine and systemic intermediate-dose methotrexate followed by loco-regional radiotherapy.

### **3. OVERVIEW OF STUDY DESIGN**

This is an open label, non randomized, phase II, multicenter, prospective trial to evaluate the safety and feasibility of the R-CHOP regimen in combination with intrathecal liposomal cytarabine and systemic intermediate-dose methotrexate followed by loco-regional radiotherapy in patients with stage I and II PTL.

#### **3.1. Statistical plan and rationale**

The previous IELSG 5 retrospective analysis on 373 patients with testis lymphoma, showed a PFS of 48% at 5 years in the entire population, regardless of the type of treatment.

The IELSG 10 prospective clinical study was designed with a sample size of 50 patients defined to reject the null hypothesis of a PFS of 50% under the alternative hypothesis that the true PFS is 70% with a 5% significance level (two-sided) and 80% power.

The early results of IELSG 10 study seem to suggest that Rituximab-CHOP regimen plus intrathecal prophylaxis with methotrexate may reduce the incidence of CNS relapses and, therefore, improve the outcome. However, the follow up is not yet adequate to allow any sound conclusion and, at present, it is unclear on which estimation of PFS should a sample size be calculated. According to the recruitment rate of the previous IELSG 10, assuming a similar number of participating centers, we may expect to enroll approximately 35 cases in 3 years. At that point, the feasibility of the design should be adequately evaluated and the follow up data from the previous IELSG 10 study should be mature enough for a careful calculation of the sample size in order to transform this pilot study in a formal phase II trial.

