### Timing

Radiation therapy will begin three weeks after the completion of chemotherapy, provided that WBC is  $>3000/\mu\text{l}$  and platelets  $>100,000/\mu\text{l}$ .

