### **10.2. Discontinuation of Treatment**

A patient should be discontinued from study treatment based on:

- Investigator discretion based on safety issues
- Progressive disease
- No response after the third course of therapy
- Any  $\geq$  grade 3 toxicity for > 2 weeks

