#### **Associated with the use of the drug**

An adverse event is considered associated with the use of the drug if the attribution is possible, probable, or very likely by the definitions listed in Section 11.1.2.

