## 11.2.2. Serious Adverse Events and SUSAR

### Reporting of SAE

All serious adverse events occurring during clinical studies must be reported **by fax** to the sponsor IELSG (IELSG Coordinating Center, CH-6500 Bellinzona – Switzerland; Phone: +[contact] – Fax: +[contact]; E-mail: [[contact]](mailto:[contact])) by investigational staff **within 24 hours** of their knowledge of the event, using the **SAE Report Forms**, which must be signed by a member of the investigational staff.

The SAE outcome must be reported within 14 days, using the **SAE Follow up Form**. In case the SAE is still ongoing after 14 days, additional SAE Follow up Forms must be sent again to report the final outcome.

The cause of **death** of a subject in a clinical study, whether or not the event is expected or associated with the investigational agent, is considered a serious adverse event. Any event requiring **hospitalization** (or prolongation of hospitalization) that occurs during the course of a subject's participation in the clinical study must be reported as a serious adverse event, except hospitalizations for:

- a standard procedure for protocol therapy administration
- social reasons in absence of an adverse event
- surgery or procedure planned before entry into the study (must be documented in the CRF)
- study drug administration
- study related procedures defined in the protocol

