### **13.2. Independent Ethics Committee or Institutional Review Board (IEC/IRB)**

Before the start of the study, the investigator will provide the IEC/IRB with current and complete copies of the following documents:

- final protocol and, if applicable, amendments
- informed consent form (and any other written materials to be provided to the subjects)

- Investigator's Brochure (or equivalent information) and amendments
- information on compensation for study-related injuries or payment to subjects for participation in the study, if applicable
- investigator's curriculum vitae or equivalent information (unless not required, as documented by IEC/IRB)
- information regarding funding, institutional affiliations, other potential conflicts of interest, and incentives for subjects
- any other documents that the IEC/IRB requests to fulfil its obligation

If study drug is being provided, it will not be shipped until after IEC/IRB has given full approval of the final protocol, amendments (if any), the informed consent form, applicable recruiting materials, and subject compensation programs, and the Investigator-sponsor has received a copy of this approval. This approval letter must be dated and must clearly identify the documents being approved.

During the study the investigator will send the following documents to the IEC/IRB for their review and approval, where appropriate:

- protocol amendments
- revision(s) to informed consent form and any other written materials to be provided to subjects
- if applicable, new or revised subject recruiting materials approved by the sponsor
- revisions to compensation for study-related injuries or payment to subjects for participation in the study, if applicable
- Investigator's Brochure amendments or new edition(s)
- summaries of the status of the study (at least annually or at intervals stipulated in guidelines of the IEC/IRB)
- reports of adverse events that are serious, unlisted, and associated with the investigational drug
- new information that may affect adversely the safety of the subjects or the conduct of the study
- deviations from or changes to the protocol to eliminate immediate hazards to the subjects
- report of deaths of subjects under the investigator's care
- notification if a new investigator is responsible for the study at the site
- any other requirements of the IEC/IRB

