For protocol amendments that increase subject risk, the amendment and applicable informed consent form revisions must be submitted promptly to the IEC/IRB for review and approval before implementation of the change(s).

At least once a year, the IEC/IRB will be informed about the clinical ongoing of this clinical study. This request should be documented in writing.

At the end of the study, the investigator (or sponsor where required) will notify the IEC/IRB about the study completion.

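### Section 11.2.1 closes adverse event reporting 30 days from the first dose, contradicting sections 9.1.1 and 9.4 and falling before most of the CNS prophylaxis is given

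*Combined protocol and SAP*

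**What the plan says.** Section 2.1 gives the primary objective: "To demonstrate safety and feasibility of the R-CHOP regimen in combination with intrathecal liposomal cytarabine and systemic intermediate-dose methotrexate", followed by radiotherapy. Section 3.1 sets the evaluation after about 35 patients: "At that point, the feasibility of the design should be adequately evaluated".

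Three sections give the adverse event window, and they differ:

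- Section 11.2.1 (All Adverse Events) starts at signed consent and stops 30 days from the first dose of study drug. It covers every event other than disease progression.
- Section 9.1.1 (Overview) requires monitoring throughout the study and until 30 days from the end of treatment.
- Section 9.4 (Adverse Events) has events reported for as long as the study lasts.

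Serious events have their own rule in section 11.2.2: "All serious adverse events occurring during clinical studies must be reported" to the sponsor, within 24 hours of the site's knowledge. That section has no 30-day limit.

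The term study drug is not fixed. Section 12.5 equates it with liposomal cytarabine, which is first given with cycle 2. A site could equally take the first dose to be the first R-CHOP cycle.

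**The concern.** The trial is meant to show that R-CHOP can be combined tolerably with intrathecal liposomal cytarabine, intermediate-dose methotrexate and radiotherapy. These additions come late in the schedule. A window that opens at consent and closes a month from the first dose records mainly the early R-CHOP cycles and misses most of what is new.

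A site working from section 11 and a site working from section 9 would record different periods. The pooled toxicity table would then mix patients followed for about a month with patients followed through the whole program, and the later components would look better tolerated than they were. Much of the tolerability evidence is not serious in the regulatory sense, for example neuropathy, mucositis or grade 3-4 laboratory changes without hospitalization, so serious event reports cannot replace it.

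**Working it through.** There is no figure in the plan to reproduce on this point. The check sets the section 11.2.1 window against the treatment calendar.

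**Inputs (Attachment 9; intrathecal cycles from section 6.1.1).** R-CHOP on days 0, 21, 42, 63, 84 and 105. Intrathecal liposomal cytarabine with cycles 2 to 5, so about days 21, 42, 63 and 84. Methotrexate on days 126 and 140. Radiotherapy on day 165.

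**Step 1: closing day under 11.2.1.** Closing day = day of first dose + 30. If the first dose is R-CHOP, 0 + 30 = day 30. If it is liposomal cytarabine, 21 + 30 = day 51.

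**Step 2: what falls inside the window.**

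| Component | Closes day 30 | Closes day 51 |
|---|---|---|
| R-CHOP cycles (6) | 2 (days 0, 21) | 3 (days 0, 21, 42) |
| Intrathecal doses (4) | 1 (day 21) | 2 (days 21, 42) |
| Methotrexate doses (2) | 0 | 0 |
| Radiotherapy, day 165 | outside | outside |

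So 3 or 2 intrathecal doses and both methotrexate doses are missed. Of the six CNS prophylaxis doses, 5 or 4 fall outside. The last intrathecal dose that is inside has 30 − 21 = 9 or 51 − 42 = 9 days of observation. Section 12.1 says a dose stays active in the CSF for at least 14 days.

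**Step 3: does the radiotherapy date matter?** Section 7 says "Radiation therapy will begin three weeks after the completion of chemotherapy", which gives 140 + 21 = day 161. Section 3.2 gives two weeks, 140 + 14 = day 154. The synopsis starts at week 24, or 24 × 7 = day 168. All are well past day 51. The exception is bilateral disease, where the synopsis and section 3.2 allow radiotherapy during R-CHOP.

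**Step 4: length of the two windows.** Section 7 allows 10 to 20 fractions. At five a week (my assumption) from day 165, treatment ends between 165 + 14 = day 179 and 165 + 28 = day 193. The section 9.1.1 window therefore runs to at least day 209 to 223. The literal 11.2.1 window covers 30/223 to 30/209 = 13 to 14% of that, or 51/223 to 51/209 = 23 to 24%.

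**Step 5: the optional pause rule.** The plan gives no tolerable rate, so every input here is an assumption. Take a Beta(0.05, 0.95) prior, look after every 5 completed patients, and pause when P(treatment-related death rate > 5%) exceeds 0.90. The boundary is 2/5, 2/10, 3/15, 3/20, 4/25. At 35 patients in 36 months, (209 to 223)/30.44 × 35/36 = 6.7 to 7.1 patients are still in the window, so 7 is used. Expected deaths = mean enrolment × rate.

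| True rate | Chance of pause | Deaths, rule | Deaths, ad hoc halt at 3rd death, lag 7 | Same, lag 4 |
|---|---|---|---|---|
| 5% | 12% | 1.65 | 1.69 | 1.66 |
| 10% | 41% | 2.86 | 2.97 | 2.80 |
| 15% | 68% | 3.60 | 3.79 | 3.42 |
| 20% | 86% | 4.07 | 4.32 | 3.75 |

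Lag 4 is an assumption that reflects deaths being reported within 24 hours and not only when a patient completes the window. At true rates of 10 to 20%, the rule saves 0.1 to 0.3 deaths against an equally slow ad hoc halt, and saves none against a quicker one.

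**The case against.** The strongest reply is that the first dose is a slip for the last dose and that nobody would act on it. Two other sections give longer windows. Sections 9.1.3 and 9.1.5 require an examination and laboratory tests before every course, methotrexate included. Section 6.2 needs toxicity graded for dosing, and section 10.2 stops treatment for grade 3 or higher toxicity lasting more than two weeks. Serious events are reported without this limit.

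Most of that stands, and it limits the loss. It does not remove the contradiction. The pre-course lists cover examination and laboratory values and do not tell a site to record new adverse events on the CRF after 11.2.1 has closed. Section 11.2.1 follows related grade 3-4 events for up to six months, but that covers events already reported, not new ones.

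Two stronger readings are tempting. A reader might infer that late serious toxicity would go unreported. Section 11.2.2 does not support that.

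A reader might also infer from section 3.1 that safety review waits for about 35 patients, so that the missing stopping rule is a defect. The sentence there concerns feasibility and does not defer safety review. SUSARs go to authorities within 7 or 15 days. Deaths and new safety information go to ethics committees, along with "summaries of the status of the study (at least annually or at intervals stipulated" in committee guidelines. Section 13.2 adds "At least once a year, the IEC/IRB will be informed about the clinical ongoing of this clinical study". Any of these could prompt a halt. It is true that none states a count that pauses registration, and that rules such as "Investigator discretion based on safety issues" in section 10.2 act on one patient. In an open-label study that section 3.1 calls a pilot, that is a design choice on which statisticians may differ.

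**Conclusion.** Section 11.2.1 is wrong as written and should be corrected. It contradicts sections 9.1.1 and 9.4 on how data for the primary objective are collected. Followed literally, it leaves out 3 or 2 of the 4 intrathecal doses, both methotrexate doses and radiotherapy at its scheduled time.

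The conclusion about the text is firm. The practical size is uncertain, because it depends on how many sites would follow 11.2.1 over section 9, which the documents cannot show. The loss is confined to non-serious events and is softened by the pre-course checks. The day counts rest on the nominal Attachment 9 schedule without delays. The percentages in step 4 also assume five fractions a week.

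The lack of a numerical pause rule carries no weight in this rating. Its expected saving over ad hoc action on 24-hour reports is small and may be nil.

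**What to change.** In section 11.2.1, replace the 30 days counted from the first dose of study drug with 30 days counted from the end of treatment, radiotherapy included, so that it agrees with section 9.1.1. A cross-reference to 11.2.1 in section 9.4 would remove the remaining difference in wording. The cost is one corrected sentence, with no new visits, and no data beyond what section 9.1.1 already requires.

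Optionally, and separately, the sponsor may add to section 3.1 a stated count of treatment-related deaths at which the coordinating center pauses new registration for review. Section 11.1.1 already treats an event as drug-associated "if the attribution is possible, probable, or very likely by the definitions listed" in section 11.1.2. The rule should apply that threshold to any part of the study therapy and exclude lymphoma deaths. The limit is the sponsor's choice, and the boundary in step 5 is one illustration. It would take a paragraph and a small table, and carries a 12% chance of a temporary pause if the true rate equals the assumed 5% limit. A count of deaths alone would not detect the neurological toxicity listed in section 1.1.2.
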